### **General considerations**

Study procedures will be performed as listed in the Schedule of Activities (Section [2](#)).

In order to allow timely sampling for PK assessments, visits for collection of the samples will be scheduled within the required time windows provided in the Schedule of Activities (Section [2](#)).

Study participants will continue to use concomitant OAMs throughout the treatment period: discontinuation or changes to dose are not permitted, except in situations where dose adjustment or complete discontinuation is required per country-specific label or when allowed per study protocol (for further details see Section [7.7.2](#)).

Study participants will be instructed to document fasting plasma glucose (FPG) each day by using the values displayed on their CGM device after waking or using a finger-stick glucose measurement. In addition, two 6-point SMPG profiles (prior to and 2 hours after the morning, midday, and evening meals) should be documented on non-consecutive days in the week prior to the required visits noted in the Schedule of Activities using CGM-based glucose values, (Section [2](#)).

Study participants who develop severe, persistent hyperglycemia based on prespecified thresholds (see Section [7.8.2.3](#)) will receive a new glucose-lowering intervention (or rescue therapy) based on clinical judgment of the investigator (see [Table BDCM.4](#)). Study participants who need rescue therapy will continue on IP in the trial until they complete all study visits.

### **Study Period 3: End-of-Treatment and Safety Follow-Up, Visits 21, 801, 802, and 803**

All randomized study participants should have a comprehensive efficacy and safety evaluation approximately 1 week after the last dose of IP and a safety follow-up visit approximately 6 weeks after the last dose of IP. During the safety follow-up study period, study participants will continue CGM and may be treated with an appropriate glucose-lowering regimen (see [Table BDCM.4](#)) if necessary. Study participants will also be required to return any remaining study diaries and used or unused IP to the investigative site.

Study participants who *complete the treatment period* will have a comprehensive End-of-Treatment efficacy and safety assessment (Week 32; Visit 21) approximately 1 week

after the last dose of IP and a safety follow-up assessment (Visit 801) approximately 6 weeks after the last dose of IP and 5 weeks after their End-of-Treatment assessment (Visit 801). During the safety follow-up study period, study participants will continue CGM, and may be treated with an appropriate glucose-lowering regimen (see [Table BDCM.4](#)) if necessary. Study participants will also be required to return any remaining study diaries and used or unused IP to the investigative site.

Study participants who *discontinue IP prior to completion* of the study for any reason should also have a comprehensive End-of-Treatment efficacy and safety assessment (Visit 802) approximately 1 week after the last dose of IP or as soon as reasonably possible thereafter, and should have a safety follow-up assessment (Visit 803) approximately 6 weeks after the last dose of IP. Study activities at Visits 802 and 803 are identical to Week 32 (Visit 21) and Visit 801, respectively.

Study participants who discontinue IP prior to study completion will be encouraged to remain in the study and to complete any scheduled study procedures that occur after their safety follow-up (Visit 803). Study participants remaining in the study will receive an appropriate rescue glucose-lowering regimen. [Table BDCM.4](#) provides details on the use of glucose-lowering medications for rescue and for treatment of acute conditions.

Study participants who *discontinue IP for any reason and are unwilling to return for a safety follow-up* visit, will be asked to perform an early termination (ET) visit as their final study visit. At this visit, study participants will perform procedures listed in the Schedule of Activities (Section 2).

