#### **Study Period 2: Treatment Period**

##### **Randomization (Week 0 [Visit 3])**

Study participants who continue to be eligible for the study will be randomized to 1 of the treatment arms. All measures to be performed at Visit 3 (see Schedule of Activities, Section 2) should be done prior to injection of the study participant's assigned investigational product (IP) to ensure that appropriate baseline measurements are obtained. Urine and serum pregnancy tests will be done before IP administration. The study participant will begin IP, if the urine pregnancy test is negative. If the result of the serum pregnancy test is positive, the study participant will be discontinued from the study (see Section 8.2).

Study personnel will inject the first dose of IP at the study site. The PK samples and ECGs at randomization must be collected as described in the Schedule of Activities (Section 2).

Following randomization, study participants will participate in a 32-week treatment period. During Weeks 1 to 8, site personnel will administer IP, and study participants will receive education and training on how to self-administer IP. The training should include information on reconstitution of IP, appropriate injection site locations, injection technique, and the signs and

symptoms of local adverse reactions, should that occur. During Weeks 9 to 12, IP will be reconstituted and administered at the site by the study participant, under supervision of trained site personnel to assure that the study participant is capable of self-administration. During Weeks 13 to 31 IP will be self-administered by the study participant at home, or optionally can be administered once weekly by site personnel. Information on self-injection can be reviewed as necessary throughout the study.

LY3209590 will be administered as one of two dose individualization algorithms ([Appendix 7](#)).

Insulin degludec will be self-administered daily by study participants after a training and first administration under site personnel supervision on Day 1 according to a modified Riddle algorithm (Section [7.2.1.2](#)).

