#### **7.2.1.2. Insulin Degludec**

Insulin degludec will be initiated at the same dose as the total daily basal insulin dose already administered, or in accordance with the locally approved product labeling if different.

Thereafter, a dosing algorithm adapted from Riddle et al. 2003 will be used by investigators for adjusting insulin degludec to target an FBG  $\leq 100$  mg/dL ( $< 5.6$  mmol/L) in order for study participants to achieve glycemic goals of an HbA1c value  $< 7.0\%$  and a pre-prandial capillary plasma glucose (PG) between 71 and 130 mg/dL (3.9 to 7.2 mmol/L; ADA 2011). In situations where study participant safety is a concern or where dose adjustments have not had the desired therapeutic effect, investigators may only make increased adjustments to the dose of insulin degludec recommended by the dose-adjustment algorithm after consultation with Lilly.

At the time of site visit or telephone visit, the investigator will assess the study participant's glycemic control for the previous week and, if necessary, inform the study participant about any needed dose adjustment. The dose will be based on the study participant's blood glucose value. Adherence to the dosing algorithm provided for this study is required from Visit 3 (randomization) up to Visit 21 (Week 32, inclusive) and will be monitored periodically by the study team. Dose increases may be made at weekly intervals and no sooner than 5 days following the last dose increase. In some cases, study participant visits could occur sooner than 5 days apart due to the allowable visit window; however, there should be no dose increase if at least 5 days have not elapsed since the previous dose increase. In contrast, the insulin degludec dose may be reduced at any time on the judgment of the investigator. Any deviations from this guidance must be approved by Lilly.

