## 7.6. Treatment Compliance

The assessment of treatment compliance with IP (LY3209590 or insulin degludec) will be determined by the following:

- Information about the once weekly IP injections will be entered into the study participant diary by the study participant and reviewed by the site personnel at each study visit. This information will be collected in the eCRF;
- IP accountability will be checked according to the Schedule of Activities (Section 2). Study participants will be instructed to return all dispensed vials, any *unused* pens and/or all empty cartons at the next visit to the study site for the purpose of performing drug accountability.

Other aspects of compliance will also be assessed at each visit, including the study participant's adherence to the visit schedule, compliance with the concomitant OAM requirements and other medication guidance (Section 7.7), completion of study diaries, results of SMBG, and any other parameters the investigator considers necessary. Study participants considered to be poorly compliant with their medications and/or study procedures (for example, missed visits or specific diagnostic tests) will receive additional training and instructions, as required.

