### **Study Participants treated with Insulin Degludec:**

Study participants assigned to the insulin degludec treatment arm will switch back to their pre-study basal insulin after Visit 21. If their pre-study Basal insulin was insulin degludec they can continue with the same dose used until Visit 21 of the study. If they switch back to another basal insulin (e.g. insulin Glargine), study participants should inject a daily dose, which is 20% lower than the last dose of insulin degludec used before Visit 21 and titrate under supervision of the investigator using the country-specific label for their pre-study basal insulin.

All study participants will continue to wear a continuous blood glucose monitor during the 5-week follow-up period to ensure a safe transition back to their pre-study basal insulin.

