#### **10.3.3.2. Secondary Analyses**

The secondary analysis will be performed on the efficacy analysis set. The main secondary efficacy analysis aims to compare LY versus Insulin Degludec with regarding to HbA1c change from baseline at Week 12 and 32. The estimand of interest is the treatment differences in HbA1c at 12 and 32 weeks while the study participants are on study treatment. The efficacy analysis set (EAS) will be used to calculate the mean difference between treatments. Similar MMRM model will be used for the main secondary analysis. The least-squares (LS) mean differences and the standard errors from each imputed sample will be calculated based on the above model, and the final estimation for the means, standard errors, 90% confidence intervals, and p-values will be reported.

A supplementary analysis will be conducted to evaluate the “treatment policy” estimand, which is defined as the treatment differences in HbA1c at 32 weeks with the randomized treatment based on FAS. The estimator is defined as the mean difference between treatments based on FAS. The missing values will be imputed using multiple imputations. The similar MMRM model will be performed on imputed data and inferences will be drawn based on the framework of multiple imputations (Rubin, 1987).

In addition to the main secondary efficacy analysis of HbA1c, the following secondary efficacy outcomes will be analyzed:

- Body weight and change from baseline to 12 and 32 weeks
- Fasting blood glucose and change from baseline at 12 and 32 weeks

The analyses of the HbA1c change, mean weight change, fasting blood glucose change and SMBG change from baseline will be conducted through MMRM similar to that of the primary efficacy outcome. The corresponding baseline will be used in the model instead of the baseline HbA1c levels. The MMRM model will also include a term for the HbA1c stratification group. The treatment p-value will be used as evidence of difference between LY3209590 and insulin degludec, while the comparison of LS means versus insulin degludec (unadjusted for multiple comparisons) and its 90% confidence interval will provide magnitude and significance of this difference.

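### Section 5.1.1 times the Week 32 assessment about a week after the last dose of IP in every arm, which conflicts with section 7.8.1 for daily degludec

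*Protocol*

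**What the plan says.** Protocol section 5.1.1, Study Period 3, sets one timing rule for everybody: "All randomized study participants should have a comprehensive efficacy and safety evaluation approximately 1 week after the last dose of IP". The next paragraph applies the same interval to those who finish treatment, names Week 32 (Visit 21), and places the safety follow-up both 6 weeks after the last dose and 5 weeks after Visit 21. Early discontinuers have Visit 802 at the same distance from their last dose. None of these sentences distinguishes the arms.

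Section 7.6 counts both drugs as IP: "The assessment of treatment compliance with IP (LY3209590 or insulin degludec) will be determined by the following". The dosing intervals differ. LY3209590 is weekly, and section 7.8.1 puts its last injection at Week 31. For the comparator, section 5.1.1 says "Insulin degludec will be self-administered daily by study participants".

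Section 7.8.1 describes the end of degludec treatment differently. "Study participants assigned to the insulin degludec treatment arm will switch back to their pre-study basal insulin after Visit 21", and of those whose pre-study basal insulin was degludec it says "they can continue with the same dose used until Visit 21 of the study". The opening paragraph of 7.8.1 has previous basal insulin resume on the evening of Visit 21. Section 7.2.1.2 adds, for degludec, "Adherence to the dosing algorithm provided for this study is required from Visit 3 (randomization) up to Visit 21 (Week 32, inclusive".

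On the analysis side, protocol section 10.3.3.2 defines the estimand as the treatment difference "while the study participants are on study treatment". SAP section 4.1 ends the efficacy analysis set (EAS) data at last dose + 10 days, the same for both drugs.

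**The concern.** The one-week rule fits a weekly product: one week is one LY3209590 dosing interval, so an LY3209590 participant is still within the last interval at Visit 21. Applied to daily degludec, the same rule means about seven dosing intervals. No section provides other basal insulin for degludec completers between Week 31 and Visit 21, because 7.8.1 starts the return to previous insulin only after that visit.

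A site therefore has two accounts of when degludec ends relative to Visit 21, and cannot follow both. Week 32 HbA1c is the primary measure and Week 32 fasting glucose is a secondary one. If some sites followed 5.1.1, the comparator alone would be measured after a gap, its glucose would tend to be higher, and the comparison would shift toward LY3209590. The change within the LY3209590 arms would not be affected. What is exposed is the difference from degludec, which SAP section 4.7 takes from the primary mixed model and protocol section 10.3.3.2 calls the main secondary efficacy analysis.

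**Working it through.** **1. Gap implied by each section.** Visit 21 falls at Week 32, day 32 × 7 = 224. A last dose at Week 31 is day 31 × 7 = 217.

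| Source | Last degludec dose | Gap before Visit 21 |
|---|---|---|
| 5.1.1, read literally | about day 217 | 224 − 217 = 7 days, roughly 6 to 7 daily doses |
| 7.8.1 | in use until Visit 21 | about 1 day or less |

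The follow-up timing confirms that 5.1.1 means a Week 31 last dose: 6 weeks after the last dose and 5 weeks after Visit 21 differ by one week, and in the Schedule of Activities Week 37 − 6 = Week 31.

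**2. Would the EAS rule remove such a value?** The cut-off is last dose + 10 days, and 7 < 10. Even at the late edge of the ±3-day window in the Schedule of Activities, 7 + 3 = 10, which does not exceed the cut-off. The value stays in the EAS and enters the primary model.

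**3. Early discontinuers.** At Visit 802 an LY3209590 participant is again about one dosing interval from the last dose and a degludec participant about seven, whichever way sites read the Visit 21 rule. Where rescue medication has already started, SAP section 4.1 excludes the later data. SAP section 4.7 does not say how Visit 802 values map to scheduled visits.

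**4. The plan's own precision, as background.** Protocol section 10.1 gives SD 1.1, margin 0.4, 300 completers (200 pooled LY3209590, 100 degludec) and two-sided alpha 0.1.

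- SE = 1.1 × √(1/200 + 1/100) = 0.1347.
- Power = Φ(0.4/0.1347 − 1.645) = Φ(1.324) = 0.907, which reproduces the stated 90%.

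The timing conflict does not change this figure or the sample size.

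**5. Size of a possible bias.** If a fraction p of degludec completers had the gap and each had HbA1c raised by d, the mean shift is p × d. The documents give neither p nor d, so the following is illustration only. At a true difference of 0.4, a one-sided 5% comparison with that margin would pass with probability Φ(−1.645 + p × d/0.1347).

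| Assumed p | Assumed d (HbA1c points) | Mean shift | Probability |
|---|---|---|---|
| any | 0 | 0 | 5.0% |
| 10% | 0.05 | 0.005 | 5.4% |
| 10% | 0.20 | 0.02 | 6.7% |
| 100% | 0.05 | 0.05 | 10.1% |
| 100% | 0.20 | 0.20 | 43.6% |

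The answer depends almost wholly on the assumed p and d. Fasting glucose does not average over earlier weeks as HbA1c does, so it would show a gap more directly.

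**The case against.** The strongest reply is that nothing tells degludec participants to stop at Week 31. Section 5.1.1 schedules visits, and the only Week 31 last-injection statement is under the LY3209590 heading of 7.8.1. Section 7.1 limits self-administration to Weeks 13 to 31 for LY3209590 only. The protocol also uses IP loosely for the weekly product: 5.1.1 speaks of reconstituting it and of once-weekly administration by site staff, then treats degludec in a separate sentence, and 7.6 goes on to refer to weekly IP injections. SAP section 4.10.1 ends exposure at the last dose for degludec but adds 7 days for LY3209590, which fits degludec continuing to Visit 21. Most of this stands. The sentence was probably written with LY3209590 in mind. That explains the conflict without removing it, because the rule is stated for all randomized participants and again for completers at the primary visit.

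Two further objections also stand:

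- Section 7.2.1.2 is weak evidence. Appendix 7 uses the same wording for LY3209590, whose last dose is at Week 31, so it does not fix a last-dose date. The conflict rests on 7.8.1.
- The error probabilities above need assumed shifts, and the large ones need every degludec completer affected. They also refer to a margin that appears only in protocol section 10.1; SAP sections 4.7 and 4.8 plan 90% confidence intervals and state no margin or non-inferiority test.

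**Conclusion.** The conflict is real and in the current text: 5.1.1 implies about 7 days from the last degludec dose to Visit 21, and 7.8.1 implies about 1 day or less. The EAS cut-off would not screen out the longer gap. Any bias would favour LY3209590 and would arise at Visit 21 only where sites followed 5.1.1 rather than 7.8.1. Its size cannot be derived from the documents; it is probably small for HbA1c after one week and more direct for fasting glucose.

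A reader might infer that the protocol plans a week without basal insulin in the comparator arm, with a safety risk attached. The documents do not support that: no section instructs it, and the gap appears only on a literal reading of 5.1.1 that 7.8.1 contradicts. A reader might also take the 10% to 44% probabilities as the cost. They rest on an unsourced shift in every degludec completer, for a test the SAP does not specify. This is a correction worth making before the Week 32 comparison is reported. It is not a defect that invalidates the design.

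**What to change.** **Protocol.** Reconcile 5.1.1 with 7.2.1.2 and 7.8.1 by stating, separately by arm, when the last dose falls relative to Visit 21 and to Visit 802. Which dosing rule applies is for the sponsor to decide. The follow-up needs no new anchor, because 5.1.1 already gives 5 weeks after Visit 21.

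**SAP.** For each degludec participant, compute the days from the last recorded dose to the Week 32 sample and report the distribution. Flag values taken after a dosing gap, with the threshold fixed before database lock. Repeat the Week 32 HbA1c and fasting glucose comparisons with flagged values set to missing, keeping earlier visits in the model. If no values are flagged, say so.

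**Cost.** One clarification letter or minor amendment and one sensitivity analysis, with no new visits. Protocol section 7.2.1 already requires the date and time of every dose in the eCRF. Because 7.6 describes diary entry only for weekly injections, check that degludec dates near Visit 21 were captured. The current SAP states that it was approved before final database lock, so the analysis can still be prespecified if lock has not occurred.

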## 5.2. Number of Participants

Approximately 536 participants will be screened to achieve 375 randomized and 300 evaluable participants for an estimated total of 100 evaluable participants per treatment group.

## 5.3. End of Study Definition

End of the study is the date of the last visit or last scheduled procedure shown in the Schedule of Activities (Section 2) for the last study participant.

## 5.4. Scientific Rationale for Study Design

This study will evaluate 2 dosing regimens of LY3209590 in study participants with T2DM who are already treated with a daily basal insulin. Study participants will take their last dose of daily basal insulin the day prior to randomization. Treatment will be initiated after randomization with either LY3209590 or insulin degludec as an active comparator. As LY3209590 has a long half-life, a weekly dosing regimen is expected to reach steady-state of PK in over **CCI** of treatment. Therefore, the withdrawal of a daily basal insulin would result in loss of glycemic control for several weeks after randomization. Therefore, a loading-dose regimen approach, by which an exposure to achieve comparable glycemic control to prior basal insulin dose can be achieved **CCI**, followed by **CCI** starting at Week 2 to maintain steady-state exposure. Subsequently, dose adjustments can be made in the initial

dose individualization phase of the study. See [Appendix 7](#) and section [7.2.1.2](#) for dosing and administration details. The 32-week treatment duration is planned as the slow dose escalation approach is necessary for LY3209590 to achieve near comparable glycemic efficacy to prior daily basal insulin.

Insulin degludec is an unblinded active comparator in this study, and will be used to compare the effects of LY3209590 on glycemic control, hypoglycemia and weight gain with a daily basal insulin.

### 5.5. Justification for Dose

Following a once-weekly SC administration of LY3209590, the time to reach steady-state glucose level is estimated between 4 to 10 weeks based on the long half-life of LY3209590. Therefore, CCI weekly dose and gradual CCI dose adjustment is recommended for LY3209590 dosing regimen. CCI of LY3209590 is based on prior basal insulin dose converting the dose in units into mg of LY3209590 and is based on PK/PD modeling of limited SAD and MAD data. Dose adjustments are based on average of prior CCI fasting glucose and hypoglycemia events. Alterations to the doses recommended by these dose adjustment algorithms are also under discretion of the investigator and will take hypoglycemia and other study participant safety concerns into account.

The starting dose for insulin degludec is the same dose as the basal insulin that the study participant used previously before entering the study. The study participant will start a titration phase based on fasting glucose achievements under this therapy and the presence of hypoglycemia or other safety concerns. The titration will be performed each week. The dose adjustment algorithm is adapted from the well-established Riddle algorithm (Section [7.2.1.2](#)) under discretion of the investigator.

Guidance is provided for the two algorithms used in dosing LY3209590. There is also guidance for conversion of prior basal insulin dose to LY3209590 loading dose, as well as dosing suggestions for investigators based on fasting glucose and hypoglycemia of the study participant ([Appendix 7](#)).

Safety of study participants will be closely monitored during the early stages of dose titration to determine whether adjustments to the conversion and dose adjustment algorithms are needed. As additional data emerges, guidance from the Sponsor on these dosing algorithms may be modified ([Appendix 7](#)).

